# **Exploratory Aims:**

**Exploratory Aim #4:** Use structural MRI, in combination with study of allelic variation in genes and associated biochemical factors associated with mood disorders (or behaviors that might contribute to or be related to mood disorders), to examine the potential modifying influence of genetic factors on volume abnormalities in children with mood disorders.

*Hypothesis 4:* The presence of the serotonin transporter (SLC6A4) promoter short ("s") allele will be associated with greater AMYG volume increases in children with mood disorders than in HC.

**Exploratory Aim #5:** Use fMRI, in combination with study of allelic variations in genes and associated biochemical factors associated with mood disorders (or behaviors that might contribute to or be related to mood disorders), to examine the potential modifying influence of genetic factors on functional abnormalities in children with mood disorders.

*Hypothesis 5:* The presence of the serotonin transporter (SLC6A4) promoter short ("s") allele will be associated with greater AMYG activation increases in children with mood disorders than in HC

In addition, we will study effects on MRI measures of allelic variation at other strongly favored candidate loci, including, for example, any specific mood disorder risk loci that may be identified over the course of the study. Exploratory analyses will also be performed for the potential modifying influence on AMYG and OFC structure and function of other demographic and clinical factors such as sex, medication exposure, current medications, presence of rapid-cycling, duration of illness, smoking history, family-loading for mood disorders, stressors and socioeconomic status.

**Exploratory Aim #6**: Use MRI, in combination with the study of allele variation in genes and associated biochemical factors and assessments of stress, to examine the potential interaction between genes and stress in influencing the development of AMYG-OFC circuitry and the emergence of disorders of mood and impulse regulation (ADHD and substance use disorders).

*Hypothesis 6A:* Adolescents with high stress exposure, as compared to adolescents with low stress exposure, will show heightened AMYG and ventral striatum response and diminished OFC response to emotional face stimuli.

*Hypothesis 6B*: Abnormal response in the AMYG-ventral striatum-OFC neural system will be associated with impulsive and addictive behaviors.

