# **MRI Data Processing:**

Image processing and analysis will be performed at the Yale MR Center on UNIX workstations using standard as well as locally developed software. Data are stripped of all identifying information and assigned a numerical code so that image processors are blind to subject information. Processing will include transformation of brains across subjects into common stereotactic space. Pre-existing subjects who had consented to share their samples and data may have their post processed MRI data along with de-identified information in computer files about their processed samples sent to the University of Iowa as part of a GWAS. Yale is not receiving information from University of Iowa for this study.

- **4. Statistical Considerations:** Describe the statistical analyses that support the study design. This section should include:
  - The number of subjects expected to enter the study.
  - A statement about the statistical power of the study to test the major hypothesis.
  - A summary of the plans for data analysis.

Hypothesis testing will be performed with region of interest measures as the dependent variables, analyzed in mixed models in consultation with a statistician, e.g. with current collaborators such as [name] (EPH) and [name] (GCRC). For example, to test hypothesis #1: diagnosis will be the between subject's variable. Hemisphere (right vs. left) and time (1st scan vs. 2nd scan) will be the within-subject variables and there will be a random subject effect. Repeated measures will be performed over the spatial domain of hemisphere. Total brain volume will be included as a covariate to control for general scaling effects. Terms that are not significant (p>0.05) will be eliminated via a backward stepwise algorithm, with the constraint that the model at each step is hierarchically well-formulated. Least squares means (Is means) and standard errors (SE) will be calculated in the mixed model and plotted to interpret significant interactions.

Whole brain analyses will also be performed to examine for group differences in regions not hypothesized *a priori*. These will be performed with widely available software such as SPM software as well locally developed software.

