#### APPROVED BY THE YALE UNIVERSITY IRB 6/15/2023

Principal Investigator: [name]

MAY 2023 HIC #0407026910

vii. orthodontic braces viii. history of claustrophobia

Follow-up visit:

Subjects will be instructed not to drink any alcohol or use any other substances within 1 week of the scanning session that could change brain function aside from use of their prescribed medication. They will be instructed to restrict caffeine use to 5 hours prior to scan. Subjects that smoke will be instructed to complete smoking cigarettes one hour prior to scanning and to then abstain from smoking until scanning has been completed.

3. **Subject Population:** Provide a detailed description of the proposed involvement of human subjects. Describe the characteristics of the subject population, including their anticipated number, age range and health status

The selection of subjects should be equitable. Generally speaking, subject selection should reflect a reasonable cross-section of the population that is being studied. In research that requires a more restricted population, the rationale for this need should be fully justified. Investigators must also provide scientific justification for the exclusion of underrepresented populations such as women, children, or minorities.

Subjects will be age 13 years or older but under age 31. We plan to include equal numbers of males and females (inclusion of sex assigned at birth) and minority subjects in proportions representative of the population in the greater New Haven area. However, specifically for the [name] sample, the adolescent cohort is primarily minority, with 60% African-American, 14% Hispanic, and 26% Caucasian.

There will be no increase to the target enrollment with the addition of the psychotherapy pilot study. Subjects already participating in the imaging component of the study will be invited to participate in a pilot treatment study, with an initial aim of piloting 10 subjects.

There will be an increase of 86 BD adolescent/young adult subjects to the target enrollment with the addition of the BE-SMART and Supplement. These subjects will be 16 to 30 years old at entry and will participate in open trials, 50% randomized to either the BE-SMART-DR or BE-SMART-ER. With an estimate of 20% attrition, there will be 26 completers per group. An additional 13 "at risk" for bipolar disorder adolescent subjects, who will not be randomized, but participate in the BE-SMART-DR psychotherapy.

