# Confidentiality of Data

Biological materials (blood or saliva) for DNA studies collected from individuals are identified by a letter and number code rather than by name. For this genetic component, the samples that are brought to [name] laboratory for storage and analysis are coded with a letter and number code that does not contain personal identifiers. Accompanying demographic information is limited to age, sex, diagnosis,

Principal Investigator: [name]

and ethnicity/race. Scans are also identified by code number. No genotype data are released to subjects or clinicians, or are recorded in the medical record, under any circumstances.

To protect subject confidentiality, subjects will be assigned a letter and number code that will be used when performing data analysis. Paper study documents that contain identifying information will be kept in a locked cabinet in a locked office in the investigator's locked research suite. The letter and number codes with the link to subject identifiers will be stored in a separate computer file on the Yale University fileserver and access will be limited to authorized personnel. This file will be backed-up in encrypted form using Yale University encryption software and will be stored on office desktop computers, as well as CDs stored in a locked file cabinet, in a locked office in the investigator's locked research suite. Some subject information will also be stored on unencrypted electronic databases, but these databases will contain only de-identified data. Laptops and computers will be pass-word protected.

After the study is closed and all data analysis is complete, all identifiers will be removed. The code will continue to be stored in a secure location to verify data should that be necessary. All other personally identifying information will be removed and deleted using the appropriate methods (e.g. zeroing). These records will be destroyed according with policies regarding length of time that research documents need to be retained after protocol completion.

Fate of DNA to be studied and issues of DNA "banking": DNA samples from participants will be retained for future study. This is clearly indicated in the informed consent. A subject or the parent/guardian of a minor subject may request that we destroy the code linking the identifiers of the subject with their DNA sample, so that the sample would only be studied anonymously from that point forward.

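### The only model described for the diagnosis contrasts does not name sex as a covariate, so a systematic sex difference between cases and controls would modestly bias the group-level comparisons (H1A, and H2A if modelled alike).

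*Combined protocol and SAP*

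**What the plan says.** Section III.4 (Statistical Considerations) sets out one model, introduced as an example for hypothesis 1:

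- Between subjects: "diagnosis will be the between subject's variable".
- Within subjects: "Hemisphere (right vs. left) and time (1st scan vs. 2nd scan) will be the within-subject variables and there will be a random subject effect".
- Covariate: "Total brain volume will be included as a covariate to control for general scaling effects". No other covariate is named.
- Model reduction: "Terms that are not significant (p>0.05) will be eliminated via a backward stepwise algorithm". The model must stay hierarchically well-formulated. No term, total brain volume included, is stated to be exempt.

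No separate model is written for the activation hypotheses (H2A, H2B).

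Sex appears in three other places:

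- Section V.3 (Subject Population) gives a recruitment aim, without saying whether it applies overall or within each diagnosis group: "We plan to include equal numbers of males and females (inclusion of sex assigned at birth".
- Section VII.2 (Confidentiality of Data) shows that sex is held: "Accompanying demographic information is limited to age, sex, diagnosis".
- Section III.1 (Exploratory Aims) lists sex among possible modifiers of amygdala and OFC structure and function: "other demographic and clinical factors such as sex, medication exposure, current medications".

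**The concern.** Cases and controls are not randomised, and they reach the study by different routes. Section V.1 describes clinician and referral-site recruitment for patients, and personal contact and advertising for controls. Nothing in the plan matches or stratifies by sex, so the two groups could have systematically different sex ratios.

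If they do, a sex effect on the imaging measure that remains after total brain volume would be counted as a diagnosis effect. Such confounding does not shrink as the sample grows. The exploratory analysis asks whether sex modifies the measures, which is a different matter from adjusting the main diagnosis contrast. The plan thus treats sex as potentially relevant to these outcomes without naming it in the one confirmatory model it describes. At stake are a modest bias in the group-level contrasts and, secondarily, a little unexplained between-subject variance.

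**Working it through.** **1. The plan's own figure.** Inputs from the Power subsection: d = 1.14 (amygdala volume), d = 0.93 (OFC change), 50 per group, 30% attrition, hence 50 × 0.70 = 35 per group. With a two-sided 5% level (assumed) and the normal approximation for two means:

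| d | n = 35 per group | n = 50 per group |
|---|---|---|
| 0.93 | 97.3% | 99.6% |
| 1.14 | 99.75% | 99.99% |

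The noncentral t gives 97.0% and 99.7% at 35 per group. The stated power above 95% reproduces.

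**2. Equal numbers overall do not guarantee balance by diagnosis.** At 50 per group, 60% female cases with 40% female controls give 30 + 20 = 50 females out of 100. With the enrolment figures in Section II.5 (396 mood disorder, 300 healthy; imaging uses a subset), equal numbers mean 348 females. If 60% of cases are female (0.60 × 396 = 237.6), the control share is (348 − 237.6)/300 = 36.8%, a gap of about 23 points. These splits are illustrations; the documents give none.

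**3. Bias in a group-level contrast.** Bias = (difference in female share) × (sex effect after total brain volume, in residual SD units). Rejection rate with no true diagnosis effect = Φ(b − 1.96) + Φ(−b − 1.96), where b = bias/√(2/n). This treats H1A as a two-group comparison of subject means. Both factors are assumed.

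| Imbalance | Sex effect | Bias | Share of d = 1.14 | Rejection, n = 35 | Rejection, n = 50 |
|---|---|---|---|---|---|
| 10 points | 0.3 SD | 0.03 SD | 2.6% | 5.2% | 5.3% |
| 20 points | 0.3 SD | 0.06 SD | 5.3% | 5.7% | 6.0% |
| 20 points | 0.5 SD | 0.10 SD | 8.8% | 7.0% | 7.9% |
| 40 points | 0.5 SD | 0.20 SD | 17.5% | 13.3% | 17.0% |

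Worked case: 0.20 × 0.5 = 0.10 SD; at n = 50, b = 0.10/√(2/50) = 0.50, giving 7.9%.

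**4. Chance imbalance.** If both groups are drawn at 50% female, the SD of the difference in female share is √(2 × 0.25/n): 10 points at n = 50 and 12 points at n = 35. A gap of 10 points or more then occurs in about 37-40% of samples. But sex variance is already in the standard error. In simulation (200,000 trials per setting, sex effect 0.3-0.5 SD), the unadjusted test rejects in 4.9-5.0%. Only a systematic difference between groups inflates the error rate.

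**5. Precision.** With an even sex split, the share of residual variance due to sex is 0.25d²/(1 + 0.25d²): 0.0225/1.0225 = 2.2% at d = 0.3 and 0.0625/1.0625 = 5.9% at d = 0.5. Removing 2-5% of the variance moves power at 35 per group from 97.3% to 97.6-97.9% for the 0.93 effect (if sex explained that share of variance in change), and from 99.75% to about 99.8% for the 1.14 effect.

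**6. Change hypotheses.** H1B corresponds to diagnosis by time in this model. A constant sex effect γ contributes γ at both scans, so it contributes γ − γ = 0 to a subject's change. A sex main effect therefore leaves that contrast essentially as it was; only a sex difference in change could confound it. The same reasoning applies to the age-related slope in H2B.

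**The case against.** The case for leaving the plan alone has several parts.

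- **The model is an illustration.** It is offered as an example, to be worked out with a statistician, in a summary for an ethics application. That stands as far as wording goes: the plan does not name sex, and a reader should not infer that it has decided to exclude it. But no other section puts sex into a confirmatory test, and leaving adjustment open until the data are seen is what pre-specification is meant to avoid.
- **Total brain volume already absorbs sex differences in volume.** Partly true for H1A, which is why only the remaining sex effect counts. It cannot be relied on for activation, and it is not itself protected from backward elimination. As no H2 model is written, the point reaches H2A only if the same model is carried over.
- **The recruitment aim may mean balance within each group.** It may; the text does not say. A reader might infer that balance is planned only overall, but the documents do not settle that, and nothing in them shows an actual imbalance.
- **Sex is examined as a modifier.** A hierarchically well-formulated diagnosis-by-sex model contains the sex main effect, so adjusted contrasts would be available. They would be exploratory, and would not be the primary test.
- **The effect is small.** Correct under the assumed inputs, and it limits the weight of the point.

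Two stronger readings are tempting. One is that all four hypotheses are biased and a sex main effect would repair them; step 6 shows that it would not adjust H1B or H2B. The other is that frequent chance imbalance makes the test invalid; step 4 shows that it keeps its 5% level.

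**Conclusion.** The point holds in a limited form. The one confirmatory model described does not name sex, sex is available, and nothing in the plan secures similar sex ratios in the non-randomised groups. The exposure is to systematic imbalance and falls on H1A, and on H2A if modelled the same way. Under the central assumptions (20-point gap, 0.3-0.5 SD residual sex effect), the bias is 0.06-0.10 SD, or 5-9% of the planned amygdala effect, with rejection of about 5.7-7.9% at a nominal 5%. It could be negligible with balanced groups, or larger under the 40-point case.

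The documents do not support a claim that the sample size is inadequate. The variance argument (about 2-6% of residual variance) is minor. This is a worthwhile low-cost improvement and does not threaten the design.

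**What to change.** In Section III.4:

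1. Name sex assigned at birth as a fixed between-subject covariate in the H1A and H2A models, exempt from backward elimination. Stating the same exemption for total brain volume, where it is used, would keep that adjustment in place too.
2. For H1B and H2B, also include a sex-by-time (or sex-by-age) term, since a main effect alone does not adjust those contrasts.
3. Report the male/female split by diagnosis group, and say in Section V.3 whether equal numbers are intended overall or within each group.

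The cost is one degree of freedom for the group-level models and two where the interaction is added. No new data are needed and the sample size does not change.

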# Purpose of the Imaging, and Integrated Imaging and Genetic Components (contains components of former HIC Protocol 11005):

## **Primary Aims:**

**Aim #1:** Use a prospective longitudinal design and structural MRI to examine age-related changes in amygdala (AMYG) and orbitofrontal cortex (OFC) volumes and to examine ventral prefrontal-amygdala neural system regional brain morphology and chemical patterns in children with mood disorders compared to a healthy comparison group of children.

*Hypothesis1A*: At both baseline and follow-up, AMYG volumes will be lower in children with mood disorders compared to healthy comparison (HC) children.

*Hypothesis 1B:* Age-related OFC volume reductions will be greater in children with mood disorders than in HC.

Exploratory analyses will also be conducted to explore the possibility of volumetric differences across diagnostic groups and in other brain regions not hypothesized *a priori*.

Aim #2: Use a prospective longitudinal design and fMRI to examine age-related changes in AMYG and

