# **Pilot MRI Data:**

Longitudinal Within-Subject Structural MRI Pilot Data:

Amygdala: 10 BD and 9 HC adolescents were scanned twice over an approximately 2-year interval. Consistent with the cross-sectional data, AMYG volumes did not decrease significantly during the 2-year interval and the diagnosis effect remained consistent, i.e. at each time point AMYG volumes were smaller in BD than in HC (p<0.05).

OFC: We used nonrigid registration methods to examine local volume changes between first and second scans within and across diagnostic groups. Consistent with our hypotheses, as well as our cross-sectional pilot data, we observed greater interval-related decreases in volume in the OFC in BD as compared to HC adolescents. Whereas HC (N=9) showed approximately 1% decrease in VPFC volume in the 2year period during adolescence (consistent with the literature on prefrontal change during this developmental period), BD (N=10) showed from 3-6% decreased in this region. Moreover, this new technique permitted us to examine whole brain to observe the particular regions of group differences. The localization of significant group differences encompassed the same regions where we have previously observed age-related changes in adolescence and functional deficits in patients with BD on both emotional and cognitive tasks.

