#### Power:

Effect sizes, calculated based upon pilot data, are large for testing of main hypotheses. For example, the mean difference in AMYG volumes between BD and HC subjects was 382 ml, corresponding to an effect size of 1.14. Mean reductions in volume in the OFC ROI of 3.35±1.73% in BD subjects compared to reductions of 0.78±3.40% in HC subjects. The absolute difference of 2.57 corresponds to a standardized effect size (d) of 0.93. A sample size of 50 subjects per group will provide >95% power to detect differences of this magnitude even at attrition rates as large as 30%.

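### Backward elimination at p>0.05 exempts no hypothesis term, so the final model for hypothesis 1 can lack the H1B estimate and the two H1A per-scan contrasts

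*Combined protocol and SAP*

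**What the plan says.** Section III, item 4 (Statistical Considerations, under MRI Data Processing) analyses region-of-interest measures in mixed models and gives one model, as an example for hypothesis 1. Diagnosis is the between-subject factor. Hemisphere and time (two scans) are the within-subject factors, with a random subject effect. On covariates: "Total brain volume will be included as a covariate to control for general scaling effects". On model reduction: "Terms that are not significant (p>0.05) will be eliminated via a backward stepwise algorithm", subject only to the model remaining hierarchically well formed. Least-squares means and standard errors are to be "calculated in the mixed model and plotted to interpret significant interactions".

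The hypotheses are under Primary Aims:
- H1A: "At both baseline and follow-up, AMYG volumes will be lower in children with mood disorders compared to healthy comparison (HC) children".
- H1B: "Age-related OFC volume reductions will be greater in children with mood disorders than in HC".

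The Pilot MRI Data section reports that "AMYG volumes did not decrease significantly during the 2-year interval and the diagnosis effect remained consistent" and, for the OFC, that "we observed greater interval-related decreases in volume in the OFC in BD as compared to HC adolescents". The Power section gives "Mean reductions in volume in the OFC ROI of 3.35±1.73% in BD subjects compared to reductions of 0.78±3.40% in HC subjects", a difference of 2.57 points (d = 0.93). It also gives an amygdala effect size of 1.14, and claims more than 95% power with 50 per group at up to 30% attrition.

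**The concern.** A term that carries a primary hypothesis should not leave the model because its p-value exceeds 0.05. No term is named as exempt here, and no other section gives a fixed model, per-scan contrasts or a rule for reporting non-significant effects.

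**H1B.** The model's only time factor is scan, and the pilot and power sections both express the OFC effect as a group difference in between-scan change. Within the stated factors that is diagnosis x time. When it is not significant, the final model contains no H1B estimate and no confidence interval, so a reader cannot tell a small effect from an imprecise one. Estimates that survive have been selected for significance.

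**H1A.** The claim concerns two time points. Once diagnosis x time is gone, the model assumes the same difference at both scans. The word *both* is then imposed by the model and not shown by the data.

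Hierarchy gives little protection. It holds diagnosis x time in the model only while the diagnosis x time x hemisphere term is retained, about 5% of the time if that term is truly null.

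**Working it through.** **1. The plan's own power figure.** Fifty per group less 30% is 35 per group. Two-sided alpha of 0.05 is assumed, because the Power section states none. Noncentrality = d x sqrt(n/2).
- d = 0.93, n = 35: 0.93 x sqrt(17.5) = 3.89, power 97.0%.
- d = 1.14, n = 35: 1.14 x sqrt(17.5) = 4.77, power 99.7%.
- d = 0.93, n = 50: 0.93 x 5 = 4.65, power 99.6%.

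The claim of more than 95% reproduces. So does d: taking the pilot's 10 BD and 9 HC, the pooled SD is sqrt((9 x 1.73² + 8 x 3.40²)/17) = 2.65. Then 2.57/2.65 = 0.970, and the small-sample correction (1 - 3/67) gives 0.926.

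**2. H1B: how often the term is deleted.** The mixed model's own standard error cannot be derived from the documents, so this is a two-sample approximation on percentage change with the Power section's SDs.

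SE = sqrt((1.73² + 3.40²)/n). A term is deleted when |estimate| is below about t(0.975) x SE.
- n = 35: SE = sqrt(14.553/35) = 0.645; threshold 1.995 x 0.645 = 1.287 points.
- n = 50: SE = sqrt(14.553/50) = 0.539; threshold 1.984 x 0.539 = 1.071 points.
- n = 100 (assumed): SE = sqrt(14.553/100) = 0.381; threshold 1.972 x 0.381 = 0.752 points.

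Simulation with 200,000 replicates per setting, sample SDs redrawn each time. True effects below 2.57 are assumptions.

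| True effect (points) | n per group | Deleted | Mean retained estimate | Average excess |
|---|---|---|---|---|
| 2.57 (pilot) | 35 | 2.5% | 2.61 | 1.5% |
| 2.57 (pilot) | 50 | 0.3% | 2.57 | 0.2% |
| 1.93 (three-quarters) | 35 | 16% | 2.11 | about 10% |
| 1.93 (three-quarters) | 50 | 6% | 1.99 | about 3% |
| 1.285 (half) | 35 | 50% | 1.79 | 39% |
| 1.285 (half) | 50 | 34-35% | 1.58 | 23% |
| 1.285 (half) | 100 | 8% | 1.35 | 5% |

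At the pilot effect, 1 minus the noncentral-t power in step 1 gives 3.0% at 35 per group and 0.4% at 50. Hence the ranges 2.5-3% and 0.3-0.4%.

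The excess is an average. At three-quarters of the pilot effect, 40% of retained estimates at 35 per group and 47% at 50 still lie below the truth.

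**3. H1A: how often the term is deleted.** If the amygdala difference is stable, as in the pilot, the true interaction is zero.
- Two-factor model: deleted with probability 0.95.
- Three-factor model: the three-way term must go first, then diagnosis x time, so 0.95 x 0.95 = 0.9025.

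A simulation used 6,000 replicates per setting, 35 per group, two scans x two hemispheres, a stable difference of 1.14 SD, no brain-volume covariate and assumed scan-to-scan correlations of 0.6, 0.8 and 0.9. It gives deletion of 90%. Both per-scan contrasts would be significant in 99.4-99.5% of studies. The final model shows a significant common difference while the two contrasts are not both significant in only 0.2-0.4%.

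**The case against.** Several points on the other side stand.

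- **The test survives.** Diagnosis x time is tested before it is removed, and removal is itself the non-significant result. A reader might infer that the rule inflates the type I error of this test; it does not.
- **Nothing says results will be withheld.** A reader might infer that non-significant H1B results or the per-scan contrasts will go unreported. The text does not say so. The sentence on least-squares means can be read as restricting only the plotting, and the pilot report shows the team giving the amygdala difference at each time point. But pilot practice is not a commitment, and the plan makes none.
- **The model is illustrative.** It is offered as an example in a summary plan, to be carried out with a statistician, and its starting interactions are not listed. It is nevertheless the only model given, and the references to hierarchy and to significant interactions show that interactions are in it.
- **H1B as diagnosis x time is an inference.** The hypothesis says age-related, and an analysis of percentage change would make it a diagnosis main effect. But the stated model has time, not age or percentage change. Under percentage change the unexempted term would be diagnosis, and the same gap would remain.
- **The imaging sample may be larger.** The enrolment section anticipates 396 mood-disorder and 300 healthy participants, with an unstated subset eligible for imaging. At an assumed 100 per group the problem shrinks, as the table shows.
- **Total brain volume.** A reader might infer that this covariate will be dropped. The text commits to including it, so the rule's unqualified wording leaves at most an ambiguity.

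**Conclusion.** The point holds as a low-to-moderate, cheaply corrected weakness in estimation and reporting. Followed as written, the rule can leave the final model without the H1B estimate. It will usually (about 90-95% of the time if the amygdala difference is stable) leave it without the two contrasts that H1A names.

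On the documents' own planning effects the practical harm is small. H1B deletion is about 2.5-3% at 35 per group and 0.3-0.4% at 50, and the H1A conclusion is almost always unchanged. The harm becomes material only if the true OFC effect is well below the pilot's. That is an assumption, though a reasonable one to examine when the pilot had 10 BD and 9 HC adolescents. It would also be tempting to say that a smaller true effect must end up either missing or exaggerated. That is true only on average: many retained estimates would fall below the truth. The H1B sizes rest on a two-sample approximation and not on the mixed model itself.

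**What to change.** In Section III, item 4, add one or two sentences:
- In the hypothesis 1 models, diagnosis, time and diagnosis x time are retained regardless of p-value.
- The amygdala group contrast at each scan (H1A) and the OFC diagnosis x time contrast (H1B) are reported with 95% confidence intervals whether or not they are significant.
- Backward elimination applies only to non-hypothesis terms, such as hemisphere interactions.

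As a clarification only, state that total brain volume is not subject to elimination.

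The cost is the wording and a few degrees of freedom. No new data or change in sample size is needed, and the power reproduced in step 1 remains above 95% at 35 per group.
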